For the accurate identification of clinical seizures, parents and caregivers will review a seizure recognition video at the time of study enrollment and retain it as a reference throughout the study. They will also be encouraged to video any suspicious events during the study period for review by clinicians of the investigation team. If at any point during the study the subject is suspected of having a clinical seizure, the parents/caregiver will be instructed to contact their site's study coordinator. The subject will be seen as soon as possible for a study visit and a video EEG will be completed for confirmation of clinical or electrographic seizure onset. Those subjects with either a documented clinical seizure on video or evidence of an electrographic seizure on video EEG will be transitioned to the Open-Label treatment phase.

At the emergence of abnormal epileptiform activity (*i.e.* sharp waves, spikes or polyspikes, spike and wave discharges, classic or modified hypsarrhythmia) prior to the onset of the first clinical or electrographic seizure, subjects will enter the protocol blinded-treatment phase (Arm A). Emergence of these specific, predetermined EEG biomarkers detected by video EEG will lead to a 1:1 randomization with vigabatrin or placebo. The vigabatrin and placebo will be dispensed as a sachet and those subjects randomized to vigabatrin will be titrated up to 100mg/kg/day by 50mg/kg/day every 3 days during the blinded phase of the study. The research pharmacist at each site will be unblinded during this phase of the study and the vigabatrin and placebo sachets doses will be identical in order to maintain the blind.

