### **Developmental Assessments:**

The developmental leadership team will oversee the implementation of the developmental assessments and monitor the quality and consistency across all sites.

All enrolled subjects, regardless of which arm of the PREVeNT protocol, will complete the Bayley-III assessment scale and Vineland -II (Survey Interview Form), at 6 months, 12 months, 24 months and 36 months of age. The Bayley Social Emotional Adaptive Behavior Assessment will be completed at the 6 month study visit. The Bayley Scales of Infant and Toddler Development, Third Edition (Bayley-III) which will be completed at 12,

24 and 36 months of age. The blind will be maintained for the clinical psychologist performing the developmental assessments throughout the study. They will be blind to treatment arm, subject's seizure control and concomitant medications. In addition to the primary outcome analysis to determine the impact of early vs. delayed treatment with vigabatrin on neurodevelopmental outcome at 24 months, the inclusion of the 12-month time-point allows additional exploratory analysis to determine if problematic areas of cognitive function and/or developmental domains are evident before 24 months of age. Additional developmental assessments will be completed which include the subdomain scores of the Bayley-III, Vineland (Survey Interview Form), Beery Visual Motor Integration (VMI), Child Behavior Check List (CBCL) and ADOS2, and/or Brief Observation of Symptoms of Autism (BOSA)\* and DSM-5 checklist at 24 months. At 36 months of age subjects will complete the same assessments as 24 months with the addition of the BOSA\* and ADI-R if the ADOS is not administered, as an exploratory analysis to assess whether changes observed at 24 months are consistent with those seen at 36 months and indicative of long-term outcome and those subjects at risk for autism or ASD. At 36 months of age subjects will also complete the Peabody Picture Vocabulary Test (PPVT). When appropriate instruments are available, measures can be administered to Spanish speaking individuals.

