**Estimate of Key timelines:**

Year 1, Q1/2: Study initiation, implementation of Data Coordinating Center, IEEG.org for EEG data transfer/ storage, and enrollment of subjects 1-4

Year 1, Q3/4: Subjects 5-28 will be enrolled=Total enrollment 28 subjects at the end of Year 1

Year 2, Q1/2: Subjects 29-52 enrolled=total 56 enrolled, Subjects 1-4 complete the 12 month visit

Year 2, Q3/4: Subjects 53-76 enrolled=total 80 subjects, Subjects 5-28- complete 12 month time point

Year 3, Q1/2: Subjects 1-4 reach the 24 month time point and Subjects 29-52 reach the 12 month time point.

Year 3, Q3/4: Subjects 5-28 complete the 24 month time point, Subjects 53-76 reach the 12 month time point

Year 4, Q1/2: Subjects 1-4 reach 36 month time point; Subjects 29-52 reach 24 month time point

Year 4, Q3/4: Subjects 5-28 reach 36 month time point, Subjects 53-76 reach 24 month time point;

\*Analysis begins for the PREVeNT trial using the baseline, 12 and 24 month data set.

Year 5, Q1/2: Subjects 29-52 reach 36 month time point,

Year 5, Q3/4: Subjects 53-76 reach 36 month time point,

\*Analysis will begin for the 36 month developmental assessments and primary and secondary outcome measures.

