## **Analyses**

The primary analyses for this Phase IIb trial consists of two testing hypotheses: time to onset of a first clinical seizure, documenting that the intervening variable (i.e. vigabatrin treatment) does indeed reduce or delay clinical seizures and comparison of the developmental outcomes at 24 months. While vigabatrin is used to control seizures and thus suppress them once seizure onset has been identified, it is presumed that if given prior to occurrence of clinical seizures occurring such a delay will be observed, but this is untested. Thus, the study endpoint of time to first clinical seizure is an essential step in determining the impact on developmental ability. The first step in the analyses will include demonstrating a difference between the proportion seizure free in the treatment arm versus placebo. This will be assessed at two years of follow-up using a chi square test and an intention to treat analysis. Supportive analyses will use a time to first seizure analysis using Cox regression methods to evaluate the treatment effects. Kaplan Meier analyses will provide graphical and overall test of the incidence of seizures. Cox models with age, gender, baseline number of epileptiform discharges included with treatment group will be attempted keeping in mind the relatively small sample size. Tests will use 2 sided Type I errors of 0.05.

The next key analysis to move to a go decision for Phase III will focus on the Bayley-III. While ideally the primary assessment would be made at age 5 or 6, there will be insufficient follow-up to make such an assessment in this grant period. We will perform assessment of the Bayley-III using the standardized cognitive scores over time using the constrained longitudinal data analysis (cLDA) method proposed by Liang and Zeger

which assumes a common mean across treatment groups at Baseline and a different mean for each treatment at each of the post-Baseline time points (12, 24, and 36 months for those who have them). In this model, we use a response vector that includes the time 0 or the baseline measure and assessments at each post-baseline observation time point. Each time point is considered a categorical variable so that no overall linear restrictions are imposed on the means over time.

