**Appendix 2: Table 1-Study Visit Schedule Enrollment and Randomization to vigabatrin or placebo**

Study Visits	Screening/Baseline (1 st visit)				Study Visits (Study Follow-up Period)											
	~6wks (1.5m)	~12wks (3m)	~18wks (4.5m)	~24wks (6m)	~12wks (3m)	~18wks (4.5m)	~24wks (6m)	~30wks (7.5m)	~36wks (9m)	~45wks (10.5m)	~52wks (12m)	~65wks (15m)	~78wks (18m)	~91wks (21m)	~104wks (24m)	~156wks (36m)
					If 6wks is BSL, then 12wks is the second visit (FU). If 12wks is BSL, then 18wks is the second visit (FU). If 18wks is BSL, then 24wks is the second visit (FU). If 24wks is BSL, then 30wks is the second visit (FU).											
Informed consent	✓	✓	✓	✓												
Eligibility Assessment	✓	✓	✓	✓												
TSC Genotype Information	✓	✓	✓	✓												
Parent's Genetic Blood Sample	✓	✓	✓	✓												
Biomarker blood collection 	✓	✓	✓	✓												
Family History & Demographics	✓	✓	✓	✓												
Medical History	✓	✓	✓	✓	✓	✓	✓	✓	✓	✓	✓	✓	✓	✓	✓	✓
Physical exam	✓	✓	✓	✓	✓	✓	✓	✓	✓	✓	✓	✓	✓	✓	✓	✓
VEEG	✓	✓	✓	✓	✓	✓	✓	✓	✓	✓	✓	✓	✓	✓	✓	✓
Concomitant Medications	✓	✓	✓	✓	✓	✓	✓	✓	✓	✓	✓	✓	✓	✓	✓	✓
Eye Exam 	✓	✓	✓	✓												
Bayley Scales of Infant and Toddler Development (3rd edition) 				✓			✓				✓				✓	✓
Beery-Buktenica Developmental Test of Visual-Motor Integration (6th edition)															✓	✓
Autism Diagnostic Observation Schedule (2nd edition)															✓	✓

Study Visits	Screening/Baseline (1 st visit)				Study Visits (Study Follow-up Period)											
	~6wks (1.5m)	~12wks (3m)	~18wks (4.5m)	~24wks (6m)	~12wks (3m)	~18wks (4.5m)	~24wks (6m)	~30wks (7.5m)	~36wks (9m)	~45wks (10.5m)	~52wks (12m)	~65wks (15m)	~78wks (18m)	~91wks (21m)	~104wks (24m)	~156wks (36m)
					If 6wks is BSL, then 12wks is the second visit (FU). If 12wks is BSL, then 18wks is the second visit (FU). If 18wks is BSL, then 24wks is the second visit (FU). If 24wks is BSL, then 30wks is the second visit (FU).											
Peabody Picture Vocabulary Test 94th edition)																✓
Child Behavioral Checklist															✓	✓
Vineland Adaptive Behavior Scale (2nd edition)				✓			✓				✓				✓	✓

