1. Follow up eye exams will be completed within 4 weeks after randomized to vigabatrin or placebo and then every 3 months. A final eye exam will be completed after subject has been off study drug for 3-6 month as per the REMS recommendations. For those patients who come off Vigabatrin at 24 months they will have to have final eye exam between 27-30 months of age.
2. Biomarker samples will be collected at each subject's enrollment, subject randomization to vigabatrin or placebo, clinical seizures onset, and a final sample after 3 months of seizure control after randomization in Arm B or 3 months of uncontrolled seizures in the open label phase of the study.
3. Bayley III (Social-Emotional and Adaptive Behavior Questionnaire) will be completed at 6 month visit and the Bayley Scales of Infant and Toddler Development, Third Edition (Bayley-III) will be completed at 12, 24 and 36 months of age.

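### The disease-modification rule cannot separate a constant effect from a growing one, and the cognitive baseline in the primary model is not tied to a time before randomisation

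*Combined protocol and SAP*

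**What the plan says.** **Model.** The Primary Study Objective makes the 24-month Bayley-III cognitive score the primary outcome. The Analyses section models it with a constrained longitudinal data analysis (cLDA) "which assumes a common mean across treatment groups at Baseline and a different mean for each treatment at each of the post-Baseline time points", the later time points being 12, 24 and 36 months. It adds: "In this model, we use a response vector that includes the time 0 or the baseline measure". The key timelines agree: "Analysis begins for the PREVeNT trial using the baseline, 12 and 24 month data set".

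**Assessments.** Under Developmental Assessments, all subjects "will complete the Bayley-III assessment scale and Vineland -II (Survey Interview Form), at 6 months, 12 months, 24 months and 36 months of age". The same paragraph continues: "The Bayley Social Emotional Adaptive Behavior Assessment will be completed at the 6 month study visit", and then places the Bayley-III itself at 12, 24 and 36 months. The schedule tables in Appendix 2 tick the Bayley row at 6 months, but their footnotes read: "Bayley III (Social-Emotional and Adaptive Behavior Questionnaire) will be completed at 6 month visit". No Bayley tick appears at the 1.5-, 3- or 4.5-month baseline visits.

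**Randomisation.** Visits follow chronological age. Randomisation follows the EEG finding: "prior to the onset of the first clinical or electrographic seizure, subjects will enter the protocol blinded-treatment phase (Arm A". Additional measures and analyses considerations puts the most common age of seizure onset at 3–7 months, and it has an analysis group randomised after 12 months.

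**Disease modification.** Further on, the Analyses section compares early differences (12 months minus baseline) with late ones (24 minus 12, or 36 minus 12), estimated from the cLDA with nominal P-values. A significant contrast is read as consistent with disease modification. No direction is given, and the choice of late difference is left open.

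**The concern.** The rule is meant to distinguish a symptomatic effect from a disease-modifying one. A symptomatic effect would be expected to appear and then hold steady; a disease-modifying effect would be expected to grow. A rule without direction, built on twice the 12-month effect minus a later effect, can be significant for either pattern, or for neither.

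The constraint on the baseline mean is justified by randomisation only for a score taken before that child was randomised. A child whose EEG trigger came at 4 months has a 6-month score that is already post-randomisation. For a child randomised after 12 months, the 12-month score, which the model treats as post-baseline, is pre-treatment. The plan does not say whose score counts as baseline, so the analyst would decide this in the model for the primary outcome.

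**Working it through.** **Inputs.** From the sample-size text: 24 per arm, effect D = 0.885 SD at 24 months, two-sided 0.05, within-child correlation ρ = 0.60 as planning value and 0.10–0.80 as range. My assumptions: compound symmetry, no missing data, the growth shapes, and the fractions f and s below.

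**Stated figure.** Two-sample t-test, 46 df, noncentrality 0.885 × √(24/2): power 85.1%. The stated 85% reproduces.

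**Disease-modification rule.** Let δ₁₂ and δ_L be the treatment differences at 12 months and at the late visit. With the baseline difference constrained to 0:

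contrast = (δ₁₂ − 0) − (δ_L − δ₁₂) = 2δ₁₂ − δ_L.

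Given baseline, each later score has variance 1 − ρ² and each pair has covariance ρ(1 − ρ), so

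SE² = (2/n)[5(1 − ρ²) − 4ρ(1 − ρ)].

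At ρ = 0.6: 5 × 0.64 − 4 × 0.6 × 0.4 = 2.24; SE = √(2 × 2.24/24) = 0.432. At ρ = 0.8 the bracket is 1.16 and SE = 0.311. At ρ = 0.1 it is 4.59 and SE = 0.618.

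*Constant effect:* the contrast is 2D − D = D with either late visit. It is flagged 29%, 52% and 80% of the time at ρ = 0.1, 0.6 and 0.8.

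*Steady growth from age s₀ months:* the effect at age a is D(a − s₀)/(24 − s₀).

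| Growth starts | Late difference | Contrast | Flagged, ρ 0.6 | Flagged, ρ 0.8 |
|---|---|---|---|---|
| Birth | 24 − 12 | 0 | 5% | 5% |
| 6 months | 24 − 12 | −D/3 = −0.295 | 10% | 15% |
| Birth | 36 − 12 | −D/2 = −0.44 | 17% | 29% |
| 6 months | 36 − 12 | −D = −0.885 | 52% | 80% |

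In the last row, growth is flagged exactly as often as a constant effect; only the sign differs, and the rule ignores the sign.

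**Baseline, if no 6-month cognitive score exists.** The common baseline mean cannot be estimated and drops out. The 24-month comparison stays unbiased at 85% power. The early difference cannot be computed as defined.

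**Baseline, if one exists and is constrained for all children.** Let f be the share randomised before 6 months and s the share of the 24-month effect already present in them. The arm difference at baseline is f·s·D, and the model subtracts ρ times it:

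estimate = D(1 − ρ·f·s), variance (2/n)(1 − ρ²).

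The documents give neither f nor s. I assume f = 0.25–0.50 and s = 0.1–0.5. At ρ = 0.6:

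- f = 0.25, s = 0.1: shrinkage 0.6 × 0.25 × 0.1 = 1.5%; estimate 0.872.
- f = 0.5, s = 0.1: shrinkage 3%; estimate 0.858; power 95.3%.
- f = 0.5, s = 1/3: shrinkage 10%; estimate about 0.80; power 92%.
- f = 0.5, s = 0.5: shrinkage 15%; estimate 0.752; power 89.0%.

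Over the same f and s, shrinkage is 2–20% at ρ = 0.8 and at most 2.5% at ρ = 0.1.

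**Only pre-randomisation scores entered.** With a valid baseline in 25%, 50% or 75% of children, power is 90%, 93% or 95% at ρ = 0.6, without bias.

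**The case against.** The best defence is that the specific text points one way. Two footnotes and two sentences limit the 6-month visit to the questionnaire; only one sentence and the footnoted ticks suggest more. On that reading the shrinkage never arises. This stands, and it is why the bias is conditional. It does not rescue the model statement, which still calls for a time-0 cognitive score.

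Even on the other reading, the bias is toward zero, the constraint is true if there is no effect, and the 15% figure needs half the effect to be present by 6 months of age. At f = 0.5, s = 0.1 and ρ = 0.6, constraining every score even has the smaller root mean squared error (0.232 against 0.252). This too stands: the remedy trades a little variance for no bias.

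The disease-modification contrast is an additional analysis with unadjusted P-values and cautious wording. It does not touch the 24-month comparison.

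A reader might infer three stronger things that the documents do not support:

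- *That no baseline cognitive score is provided.* The documents contradict each other on this; they do not settle it.
- *That the rule misses growing effects generally.* Low detection holds for 24 minus 12. With 36 minus 12, growth from 6 months is flagged as often as a constant effect.
- *That site stratification replaced the age strata.* The Data and Monitoring Plan describes what its system usually does, which does not exclude the strata of ≤7 and >7 months in the Protocol description.

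**Conclusion.** The rule is wrong as written. It labels a constant effect as consistent with disease modification 52–80% of the time at ρ 0.6–0.8 (29% at 0.1), and its answer for a growing effect depends on an unspecified choice of late visit. These rates assume compound symmetry and, for growth, the shapes shown. The consequence is confined to an exploratory claim.

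The baseline definition is incomplete in the model for the primary outcome. The 24-month estimate is biased only if a 6-month cognitive score exists and is constrained for children randomised before it. The bias is then toward zero, about 1.5–15% at ρ 0.6 under the assumed fractions. No stated power figure is wrong.

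A secondary point: the analysis groups split at 12 months are not the randomised age strata (≤7 and >7 months).

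**What to change.** These are wording changes before unblinding, with no new visits.

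1. **6-month assessment.** Reconcile the first Developmental Assessments sentence and the schedule ticks with the sentences that follow and the table footnotes.
2. **Baseline.** Keep the cLDA. Enter a cognitive score as baseline only if it precedes that child's randomisation; otherwise treat baseline as missing. If no child has one, fit arm-by-visit means at 12, 24 and 36 months. Do not count a 12-month score taken before randomisation toward the 12-month treatment difference. *Cost:* up to about 2 points of power when little effect is present by 6 months (95.3% to 93.0% at ρ 0.6, f = 0.5, s = 0.1). At f = s = 0.5 the change gains power instead (89.0% to 93.0%).
3. **Disease modification.** Name one late difference. Require the lower 95% limit of (later treatment difference minus 12-month treatment difference) to exceed 0, among children randomised before their 12-month score, and keep it exploratory. Without that restriction, an assumed 10–25% randomised after 12 months would make a constant effect look like growth of 0.09–0.22 SD (0.885 × 0.10 to 0.25). *Cost:* limited power. For 24 minus 12 and growth of 0.44 SD it is 39–66% at 24 per arm (ρ 0.6–0.8), and 30–53% if the restriction leaves an assumed 18 per arm.
4. **Strata.** Include the randomised age stratum (≤7/>7 months) as a covariate, use it in place of or beside the 12-month split, and reconcile it with the site-stratification text.

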### **Vigabatrin and Placebo:**

The investigational drug product to be used in this study is vigabatrin, marketed in the US under the trade name Sabril by Lundbeck Pharmaceuticals. Lundbeck will supply vigabatrin for this study directly to the Investigational Pharmacy at Cincinnati Children's Hospital (CCHMC). It is supplied as a white granular powder enclosed in 50x60 mm child-resistant aluminum foil packets (sachet). It is non-hygroscopic, freely soluble in water, and thermodynamically stable with an established shelf life of more than 36 months at room temperature. Povidone is the primary inactive excipient. The investigational pharmacy at CCHMC will produce identical white granular powder with indistinguishable

physical appearance, color, solubility, and taste to the vigabatrin powder supplied by Lundbeck. Both vigabatrin and placebo will be repackaged into identical aluminum foil sachets so as to maintain treatment blinding and distribute as appropriate to the investigational pharmacies at local participating sites for individual patient distribution and administration. For administration, the entire content of one sachet (500 mg active drug) is dissolved in 10 ml water for oral administration that is dosed according to body weight 50-150 mg/kg/day divided BID. Dosing will follow established recommended guidelines (50 mg/kg/day and increased as needed by 50 mg/kg/day every 3 days up to a maximum dose of 100 mg/kg/day, divided BID in the blinded phase and 150mg/kg/day in the Open Label Phase).

Subjects randomized to vigabatrin in Arm A (Figure 1) will be treated with vigabatrin 100mg/kg/day or placebo until 24 months of age or until they show evidence of clinical seizures or electrographic seizures on video EEG. Based on the published EEG biomarker data for infants with TSC, the subjects randomized to our primary randomized trial population, Arm A (who have evidence of epileptiform activity in their EEG) will be at high risk for developing epilepsy (approaching 100%).

If the subjects in Arm A are seizure free at 24 months of age, they will be tapered off the study drug (vigabatrin or placebo) without breaking the treatment blind and continue to be followed for the duration of the study (36 months).

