If electrographic or clinical seizures occur while on study drug, they will transition into the Open label phase of the study (Arm B) and continue to be followed until 36 months of age as per the PREVeNT protocol schedule. If the seizures are not controlled in the Open label phase at the vigabatrin maximum dose of 150mg/kg/day, the investigator may change the antiepileptic medication as clinically warranted to improve seizure control (including tapering off vigabatrin). These subjects will remain in the open arm of the study for the duration of the protocol (36 months).

Based on the TSC-EBS data, it is estimated that 30% of subjects (24 subjects) in Arm C will not be treated but continue in the study until the age of 36 months (Table 2).

See Pharmacy Manual for details of packaging and labeling, product tracking and accountability, and product disposal and destruction.

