A second consideration is the observation time during the trial. Since the patients will be put on active therapy following an event, a second consideration is the duration of seizure suppression, that is, the time after an event has occurred up until two years. This is effectively, the medication possession ratio ( $MPR = \text{total time on vigabatrin treatment} / \text{total follow-up time}$ ). We expect the delayed treatment group on average to have Vigabatrin treatment for slightly less than 1-2 years and effectively 2-3 years for early treatment group. This is based on assuming a uniform distribution of occurrence of the clinical seizures. Clearly, if there were no significant differences between the early and late treatment in this parameter, we would expect a negative outcome. However, this parameter may be useful in understanding the extent of the differences observed. The MPR, if there is a relationship to the primary outcome, may be useful for imputation of missing data (which we expect to be quite low). This variable can be entered into the cLDA model and assessed using the procedures of MacKinnon for testing mediation. The mediation model would say that the effect of the treatment on the outcome of the cognitive scores is mediated through the MPR and not the earlier intervention. The sample size may not allow a clear answer to this question, but if earlier intervention before the onset of a clinical seizure is key in preservation of cognitive function, then the mediation will not be demonstrated.

Drug resistant epilepsy: For the current study, drug resistant epilepsy is defined as the “failure of adequate trials of two tolerated appropriately chosen and used antiepileptic drug schedules (whether as monotherapy or in combination) to achieve sustained seizure freedom as put forth by the International League Against Epilepsy. This will be compared between the early and delayed treatment groups using Fisher’s exact test.

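### The medication possession ratio has no consistent time window, and the 2-3 years of vigabatrin expected in the early group conflicts with the protocol's own start and stop rules

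*Combined protocol and SAP*

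**What the plan says.** All in the Analyses section unless noted.

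- A second consideration is introduced as "the time after an event has occurred up until two years".
- This is then equated with MPR, defined as "total time on vigabatrin treatment" divided by "total follow-up time". The formula has no end date.
- Expected average exposure in the delayed group, then the early group, is "Vigabatrin treatment for slightly less than 1-2 years and effectively 2-3 years for early treatment group". The stated basis is "assuming a uniform distribution of occurrence of the clinical seizures".
- MPR is offered as a plausibility check: "if there were no significant differences between the early and late treatment in this parameter, we would expect a negative outcome". It is also a candidate mediator of the cognitive effect and a possible imputation variable.
- Under Vigabatrin and Placebo: "If the subjects in Arm A are seizure free at 24 months of age, they will be tapered off the study drug". These children are still followed to 36 months. Under Protocol description, vigabatrin may be started if they seize later.
- Children who seize on study drug have a different path: "they will transition into the Open label phase of the study (Arm B) and continue to be followed until 36 months of age". The same section lets the investigator stop vigabatrin if seizures remain uncontrolled.
- Under Protocol description, randomisation takes place when epileptiform activity emerges. The first scheduled EEG in Appendix 2, Table 1 is at about 1.5 months.
- Under Study Objectives, the primary outcome is the Bayley-III cognitive score at 24 months.

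**The concern.** There are two separate faults.

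**Expected exposure.** The early-group figure of 2-3 years does not fit rules that start drug at biomarker emergence and end it at 24 months in children who stay seizure free. The plan expects 19 of 24 early-arm children to be in that position.

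**Window.** One sentence stops the clock at two years and the next divides by all follow-up, which runs to 36 months. Two analysts could build quite different variables from this text. On the longer window a child in whom prevention worked spends the third year off drug by design, while a child who seized may spend it on drug. The ratio would then fall when treatment succeeds, and would include exposure that came after the score it is meant to explain.

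At stake are the reading of the plausibility check, the mediation model, and any imputation of 24-month scores that uses MPR.

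**Working it through.** **Inputs from the documents.** Seizure proportions by 24 months: early pE = 5/24 = 0.208 (alternative 10/24 = 0.417), placebo pP = 22/24 = 0.917, with 24 per arm (Primary Study Objective, statistical section). Seizure times are uniform, taken here between randomisation and 24 months.

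**Assumptions, not in the documents.** Age at randomisation r (varied from 1.5 to 12 months) and the share of open-label children who stay on vigabatrin. The two-week transition and any restart after 24 months are ignored.

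**1. Reproducing the plan's figures.** Put r = 0, no taper, and horizon H of 24 or 36 months.
- Delayed: pP × (H − 12)/12 = 0.917 × 1 = 0.92 years, or 0.917 × 2 = 1.83 years. This matches the plan's delayed range.
- Early: H/12 = 2 or 3 years. This matches only as continuous drug from birth with no taper.

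So the delayed range reproduces under that simplification. The early range needs conditions the protocol rules out for seizure-free children.

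**2. Blinded drug in a seizure-free early-arm child** = 24 − r. That is 22.5 months (1.9 years) at r = 1.5, 18 at r = 6, 17 (1.4 years) at r = 7, and 12 at r = 12.

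**3. Early-arm mean to 36 months, full open-label retention** = (24 − r) + 12 × pE. At 5/24 this is 26.5 − r, so it reaches 24 months only if r ≤ 2.5. At 10/24 it is 29 − r, so r ≤ 5.

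**4. MPR on the 36-month window** (denominator 36 − r).

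Single children, r = 7: a prevention success scores 17/29 = 0.59. A placebo child who seizes at 9 months and stays on drug scores 27/29 = 0.93.

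Arm means, full retention: early [(24 − r) + 12pE]/(36 − r); delayed pP × [36 − (r + 24)/2]/(36 − r).

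| r (months) | Early, months | Delayed, months | MPR early vs delayed |
|---|---|---|---|
| 1.5 | 25.0 | 21.3 | 0.73 vs 0.62 |
| 6 | 20.5 | 19.25 | 0.68 vs 0.64 |
| 7 | 19.5 | 18.8 | 0.67 vs 0.65 |
| 9 | 17.5 | 17.9 | 0.65 vs 0.66 |
| 12 | 14.5 | 16.5 | 0.60 vs 0.69 |

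The arms are equal where 26.5 − r = 22 − 0.458r, that is r = 4.5/0.542 = 8.3 months. The sign reverses beyond that.

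Half the open-label children stopping 6 months after seizure, r = 7 (mean seizure age 15.5):
- Delayed: 0.917 × (0.5 × 20.5 + 0.5 × 6) = 12.1 months; 12.1/29 = 0.42.
- Early: 0.792 × 17 + 0.208 × (0.5 × 29 + 0.5 × 14.5) = 18.0 months; 18.0/29 = 0.62.

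Simulated chance that a two-sided 5% Welch t-test finds an MPR difference (r = 7, 24 per arm):
- full retention: about 6%;
- a quarter stopping (0.65 vs 0.53): about a third;
- half stopping: about 82%;
- 10/24 early seizures with full retention (0.76 vs 0.65): about 35%.

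If vigabatrin prevented nothing (22/24 seizing in both arms, full retention, r = 7), the early mean would be 17 + 12 × 0.917 = 28.0 months, so 28.0/29 = 0.97 vs 0.65. On this window and with full retention, the contrast is larger when treatment fails than when it works as planned.

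**5. MPR on a 24-month window** (r = 7, full retention). Early: 17/17 = 1.00 (1.4 years). Delayed: 0.917 × 8.5 = 7.8 months (0.65 years), and 7.8/17 = 0.46. If half stop after 6 months it is 0.98 vs 0.36. With no efficacy and full retention it is still 1.00 vs 0.46.

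**The case against.** The formula never says 36 months. The preceding sentence names two years, and on that reading the arms separate clearly (1.00 vs 0.46). This stands: the defect is an undefined, self-contradicting window, not a fixed wrong one. Still, 36 months is the literal sense of all follow-up, and an exposure above two years needs a horizon beyond 24 months.

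The 2-3 years is a group average, while the 22.5-month cap applies to one subgroup. Early-arm children who seize and stay on drug can exceed two years, and a restart after 24 months is allowed. This also stands, but the cap covers 19 of 24 expected children, and the arm mean still needs randomisation by about 2.5 months (5 months at 10/24).

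A reader might infer that the arm contrast almost vanishes on the plan's own assumptions, or that the choice of denominator is what makes 2-3 years unreachable. The documents support neither. The near-zero contrast needs randomisation near 7 months and full open-label retention, which the plan does not state and which its allowance for stopping vigabatrin makes doubtful. The exposure figure fails because of the biomarker wait and the 24-month taper, whatever the denominator.

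Finally, the plan presents MPR tentatively and concedes that the sample may not answer the mediation question. The longitudinal model also includes 36-month scores, for which later exposure is relevant.

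**Conclusion.** The point holds as an inconsistency that should be corrected. The early-group expectation of 2-3 years conflicts with the protocol's start and stop rules: seizure-free children have at most about 22.5 months of blinded drug, barring a later restart. The MPR window is contradictory. Its literal reading counts drug taken after the 24-month outcome, an objection that needs no assumption about randomisation age or retention.

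The size of the arm contrast on the 36-month window is not determined by the documents. At the planned seizure rates with full retention, the difference runs from about +0.11 (randomisation at 1.5 months) to −0.08 (12 months). With half stopping after 6 months and randomisation at 7 months it is +0.20. A null result on the plausibility check could therefore occur in a trial that works as designed, but it would be wrong to say that it must.

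The sample size and the primary test are unaffected.

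**What to change.** 1. For any use with the 24-month Bayley-III, define MPR as time on vigabatrin from randomisation to the 24-month assessment, divided by time from randomisation to that assessment, in both arms.
2. Report exposure from 24 to 36 months separately, and use it only with 36-month scores.
3. Replace both expected-exposure ranges with figures derived from the protocol's rules, stating the assumed randomisation age and retention. To 24 months, for randomisation at 7 months and full retention, these are about 1.4 years early and 0.65 years delayed.
4. State the limitation. On this window early-arm MPR is close to 1 whether or not treatment works, so an arm difference shows only that exposure separated, and mediation through MPR can barely be told apart from assignment. The sentence linking a null MPR difference to a negative trial should be reworded to match.

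The cost is SAP wording and two corrected figures. No new data are needed, and no treatment rule changes.
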